10.3. Efficacy analysis

Name of data	Derivation and calculation methods																											
Improvement in DAS28-4/ESR by EULAR Response Criteria	
Improvement in DAS28-4/ESR should be calculated in accordance with EULAR Response Criteria.
 
EULAR Judgment criteria for improvement in DAS28 (4/ESR)
 
  
 	Improvement in DAS28#1	
 
 	>1.2	>0.6 and ≤1.2	≤0.6	
   
 DAS28 at the time of assessment	≤3.2	Good response	Moderate response	No response	
 
 >3.2 and ≤5.1	Moderate response	Moderate response	No response	
 
 >5.1	Moderate response	No response	No response	
  
 
#1Improvement in DAS28: (DAS28 at the start of Humira treatment) - (DAS28 at the time of assessment)
 
Good Response and Moderate Response should be considered effective, and No Response as ineffective.
							Improvement in DAS28 #1					>1.2	>0.6 and ≤1.2	≤0.6	DAS28 at the time of assessment	≤3.2	Good response	Moderate response	No response	>3.2 and ≤5.1	Moderate response	Moderate response	No response	>5.1	Moderate response	No response	No response
		Improvement in DAS28 #1																										
		>1.2	>0.6 and ≤1.2	≤0.6																								
DAS28 at the time of assessment	≤3.2	Good response	Moderate response	No response																								
	>3.2 and ≤5.1	Moderate response	Moderate response	No response																								
	>5.1	Moderate response	No response	No response																								
Remission	
For DAS28-4/ESR, CDAI and SDAI, cases meeting the following conditions should be handled as remission.
 
 
• Where DAS28-4/ESR is <2.6, remission is “Yes”.
 
• Where CDAI is ≤2.8, remission is “Yes”.
 
• Where SDAI is ≤3.3, remission is “Yes”.
 
 
See the definition document for analytical dataset as setting of the presence or absence of efficacy is conducted at the time of the creation of analytical dataset.
 
Name of analytical dataset: A_EFF2
 
Names of variables: AVAL_ESR_1, AVAL_CDAI, AVAL_SDAI
																											
DAS28 disease activity	
For DAS28-4/ESR, categories of disease activity are shown as follows:
 
 
• Remission DAS28-4/ESR <2.6
 
• Low disease activity: 2.6 <=DAS28-4/ESR <3.2
 
• Moderate disease activity: 3.2 <=DAS28-4/ESR <5.1
 
• High disease activity: 5.1 <=DAS28-4/ESR
 
 
Name of analytical dataset: A_EFF2
 
Name of variable: AVAL_ESR_1
																											

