**1. Purpose of the surveillance**

This postmarketing surveillance of Humira® for Subcutaneous Injection (generic name: adalimumab (recombinant)) will be conducted to clarify the following with regard to the treatment of juvenile idiopathic arthritis (JIA) affecting multiple joints with this drug:

- ① Unknown adverse drug reactions (ADRs) (especially important ADRs)
- ② Incidence and conditions of occurrence of adverse reactions in the clinical setting
- ③ Factors that may affect the safety and efficacy of Humira

< Items of investigation of particular interest>

Development of infections, tuberculosis, malignant tumor, administration site reactions, autoimmune diseases, pancytopenia, demyelinating disease, congestive heart failure, and interstitial pneumonia

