Patients excluded from the efficacy analysis set	
Of the patients included in the safety analysis set, those who meet any of the following from the list of inclusion of patients.
 
 
Disease not eligible to the survey
 
Disease defined as not eligible to the survey in the implementation plan
 
Patient ineligible for efficacy assessment
 
DAS 28 (4/ESR) cannot be calculated at any time points after administration of Humira
 

Patients included in the efficacy analysis set	Patients included in the safety analysis set excluding patients excluded from the efficacy analysis set.

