### 13.3. Efficacy

“Table 3.1 DAS28 remission rates by background factor”

Analysis object: Patients included in the efficacy analysis set

Purpose of analysis: For DAS28-4/ESR, the number of patients who remitted and the remission rate will be calculated in accordance with “11. Data-layer separation” (age 1, age 2, age 3, sex, body weight, BMI, reason for use and type of disease, disease duration 2, complications, complication: liver disorder, complication: renal disorder, complication: cardiovascular disorder, complication: blood disorder, complication: respiratory disorder, complication: other, past medical history, history of allergy, Steinbrocker Staging System, Steinbrocker Functional Classification, administration method category, previous medications, status of previous medication: biological product, status of previous medication: MTX, status of previous medication: corticosteroid, status of previous medication: NSAIDs, status of previous medication: Other DMARDs, concomitant drugs, status of concomitant drug: MTX, status of MTX: details, status of concomitant drug: corticosteroid, status of concomitant drug: NSAIDs, status of concomitant drug: Other DMARDs).

For the remission rates, Fisher's exact test should be conducted when the

background factor is a nominal scale and Mann-Whitney U test should be conducted when the background factor is an ordinal scale.

Notes: • Reason for use and type of disease may be redundantly aggregated. No test will be conducted for this item.

“Table 3.2.1 Remission rates in patients switched to other biological products”

Analysis object: Patients included in the efficacy analysis set

Purpose of analysis: For DAS28-4/ESR, the number of patients, the number of patients remitted and the remission rate will be calculated on the basis of the number of patients switched to other biological products and the breakdown of the reasons for switching (remission, subtherapeutic response, onset of adverse events, patient's request, no hospital visit [including hospital transfer], other).

Notes: • The breakdown of the reasons for switching may be redundantly aggregated.  
• “Onset of an adverse event” should apply only when “Onset of an adverse event” is selected and an adverse event during safety analysis period has occurred.

“Table 3.2.2 Remission rates in combination therapy for juvenile idiopathic arthritis”

Analysis object: Patients included in the efficacy analysis set

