Purpose of analysis: For DAS28-4/ESR, the number of patients, the number of patients remitted and the remission rate will be calculated on the basis of combination therapy for juvenile idiopathic arthritis (no, yes, unknown/unspecified). For patients receiving combination therapy, the number of patients, the number of patients remitted and the remission rate by breakdown of combination therapy (rehabilitation, other, unknown) will be calculated.

Notes: The breakdown of combination therapy may be redundantly aggregated.

“Table 3.2.3 Remission rates by duration of combination use of MTX for juvenile idiopathic arthritis”

Analysis object: Patients included in the efficacy analysis set

Purpose of analysis: For DAS28-4/ESR, the number of patients remitted and the remission rate will be calculated on the basis of combination use of MTX for juvenile idiopathic arthritis (no, yes, unknown/unspecified). Where there is a duration of combination use of MTX, the number of patients, the number of patients remitted and the remission rate by breakdown of duration of combination use (after the start of Humira treatment up to the end date of Humira treatment, at least a dose used during Humira treatment, unknown/unspecified) will be calculated.

Notes: The breakdown of duration of combination use may be redundantly aggregated.

“Table 3.3 Changes in anti-CCP antibodies”

Analysis object: Patients included in the efficacy analysis set

Purpose of analysis: For anti-CCP antibodies, the basic statistics of values measured before the start

of treatment and at 24 weeks after the start of treatment will be calculated in accordance with “12. Handling of data on tests/timing of assessment” (time window for efficacy assessment). Basic statistics will also be calculated for the amount of change from before the start of treatment, and a paired t-test will be conducted.

Note: None in particular.

“Table 3.4.1 Changes in DAS 28-4/ESR”

Analysis object: Patients included in the efficacy analysis set (DAS28-4/ESR)

Purpose of analysis: For DAS28-4/ESR, the basic statistics of values measured before the start of treatment, at 4, 8, 12, 16 and 24 weeks after the start of treatment, and at the final assessment will be calculated in accordance with “12. Handling of data on tests/timing of assessment” (time window for efficacy assessment). Basic statistics will also be calculated for the amount of change from before the start of treatment, and a paired t-test will be conducted.

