the final assessment, the number of patients who showed efficacy and the efficacy rate will be calculated in accordance with “11. Data-layer separation” (age 1, age 2, age 3, sex, body weight, BMI, reason for use and type of disease, disease duration 2, complications, complication: liver disorder, complication: renal disorder, complication: cardiovascular disorder, complication: blood disorder, complication: respiratory disorder, complication: other, past medical history, history of allergy, Steinbrocker Staging System, Steinbrocker Functional Classification, administration method category, previous medications, status of previous medication: biological product, status of previous medication: MTX, status of previous medication: corticosteroid, status of previous medication: NSAIDs, status of previous medication: Other DMARDs, concomitant drugs, status of concomitant drug: MTX, status of MTX: details, status of concomitant drug: corticosteroid, status of concomitant drug: NSAIDs, status of concomitant drug: Other DMARDs).

For the efficacy rates, Fisher's exact test should be conducted when the background factor is a nominal scale and Mann-Whitney U test should be conducted when the background factor is an ordinal scale.

Notes: • Reason for use and type of disease may be redundantly aggregated. No test will be conducted for this item.

“Table 3.5.3 Remission rates assessed by DAS28-4/ESR by reason for use and type of disease”

Analysis object: Patients included in the efficacy analysis set

Purpose of analysis: For DAS28 disease activity, the number and percentage of patients will be calculated on the basis of DAS28 disease activity before the start of treatment, at 4, 8, 12, 16 and 24 weeks after the start of treatment, and at the final assessment in accordance with “11. Data-layer separation” (reason for use and type of disease” and “12. Handling of data on tests/timing of assessment” (time window for efficacy assessment). The 95% confidence interval of the remission rates will also be calculated.

Notes: Patients with more than one reason for use and type of disease will be redundantly aggregated for each type of disease.

As the analysis object is patients included in the efficacy analysis set, oligoarthritis (persistent) will be excluded.

“Figure 3.5.3.1 Remission rates assessed by DAS28-4/ESR by reason for use and type of disease (overall)”

Analysis object: Patients included in the efficacy analysis set

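### Table 3.1 tests factors for DAS28 remission without regard to baseline DAS28, so a factor linked only to baseline activity can look like an efficacy factor

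*SAP*

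**What the plan says.** - **Objective.** Protocol section 1 lists among the aims "Factors that may affect the safety and efficacy of Humira". SAP section 4.1 repeats this as its third purpose.
- **Remission.** SAP section 10.3: "For DAS28-4/ESR, CDAI and SDAI, cases meeting the following conditions should be handled as remission". The DAS28-4/ESR condition is a value below 2.6. Nothing is required of the baseline value or of the change.
- **Table 3.1.** SAP section 13.3: "For DAS28-4/ESR, the number of patients who remitted and the remission rate will be calculated in accordance with" a list of 32 background factors. Each is tested alone by Fisher's exact or Mann-Whitney test, except disease type, which is not tested. Steinbrocker stage and class are on the list; baseline DAS28 is not. No time point is named, nor in Tables 3.2.1–3.2.3 (for example "the number of patients remitted and the remission rate will be calculated on the basis of combination therapy" in Table 3.2.2).
- **Table 3.5.2.** The same 32 factors, for EULAR response, with the time point stated: "the final assessment, the number of patients who showed efficacy and the efficacy rate will be calculated in accordance with" the list. Improvement here is a difference, "DAS28 at the start of Humira treatment) - (DAS28 at the time of assessment", and a fall of 0.6 or less is no response.
- **Efficacy set.** Among the exclusions in SAP section 8 is "DAS 28 (4/ESR) cannot be calculated at any time points after administration of Humira". No baseline DAS28 is required.
- **Where baseline activity appears.** Table 3.4.1 summarises it overall. In Table 3.5.3, by disease type, "the number and percentage of patients will be calculated on the basis of DAS28 disease activity before the start of treatment" and at each later time point.

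**The concern.** An absolute cut-off measures where a patient ends, which depends on where the patient began as well as on the response to Humira. If one level of a factor (an age band, prior biologic use, concomitant MTX) tends to go with a lower baseline DAS28, its remission rate will be higher even when the drug works identically at every level. Table 3.1 would show this as a significant factor, and nothing in the planned output would let a reader tell it from a difference in response. Table 3.5.3 cannot settle the matter, because it shows baseline by disease type, the one factor that is not tested.

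At stake is the reading of the survey's objective on efficacy factors. The total remission rate is a lesser matter: patients already below 2.6 at the start, or with no baseline value, are counted in it without being identified.

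**Working it through.** **The plan's own figure.** The documents give no figure on this point. The only sizing statement (Protocol section 2) concerns adverse drug reactions: 1 − 0.97^100 = 0.952, which reproduces the stated 95% but says nothing about the efficacy tests.

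**Inputs from the documents.** About 100 patients (Protocol section 2); two-sided 5% (SAP 9.14); Fisher's exact test, remission <2.6 and the EULAR table (SAP 10.3, 13.3).

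**Assumed, not in the documents.** A two-level factor, 50 v 50. Baseline DAS28 normal with SD 1.3 and mean 4.0 or 4.75 in the higher group; the other group is lower by 0, 0.5 or 1.0. Change has SD 1.0, with a mean fall of 1.5 points or 35% of baseline. The factor acts on baseline only.

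**Step 1: dependence on baseline.** With a mean fall of 1.5, the chance of remission given baseline b is Φ((2.6 − b + 1.5)/1.0) = Φ(4.1 − b).
- b = 2.6: Φ(1.5) = 93%
- b = 3.5: Φ(0.6) = 73%
- b = 5.5: Φ(−1.4) = 8%

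The gradient runs through the whole range above 2.6.

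**Step 2: group rates.** The final value has SD √(1.3² + 1.0²) = 1.640.
- Means 4.75 v 3.75, fall 1.5 in both: Φ((2.6 − 3.25)/1.640) = 35% v Φ((2.6 − 2.25)/1.640) = 58%.
- Means 4.0 v 3.0, no mean change in either: Φ(−1.4/1.640) = 20% v Φ(−0.4/1.640) = 40%. Here Humira does nothing on average, and the factor still appears to double remission.

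**Step 3: how often p<0.05.** Simulation, 4,000 surveys per setting (simulation error at most √(0.25/4000) = 0.8 points). Ranges cover the two baseline means.

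| Remission test | Difference 0.5, fall 1.5 | Difference 0.5, fall 35% | Difference 1.0, fall 1.5 | Difference 1.0, fall 35% |
|---|---|---|---|---|
| Fisher, as planned | 18% | 11–13% | 59–62% | 43–44% |
| Fisher, baseline ≥2.6 only | 10–12% | 7–9% | 23–36% | 14–22% |
| Mantel-Haenszel, <2.6 v ≥2.6 | 8–10% | 6–7% | 20–32% | 12–20% |
| Mantel-Haenszel, four SAP categories | 3% | 3% | 4% | 4% |

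With no baseline difference the planned test rejects in 3–4%. The Mantel-Haenszel rows use the continuity correction; without it the four-category rows run from 5% to 8%. A logistic model with continuous baseline DAS28 gives 5–7%.

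**Step 4: EULAR response, same settings.** Fisher rejects in 3–4% when the fall does not depend on baseline. With a 35% fall it rejects in 5–6% (difference 0.5) and 12–17% (difference 1.0), and in the other direction: with means 4.0 v 3.0, response is 76% v 65%, the lower-baseline group doing worse.

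**The case against.** The best counter-arguments are these.

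- **Patients have active disease.** SAP section 4.2 requires active joint disease with poor response to existing treatment. This bears on how many patients start below 2.6, but it sets no DAS28 minimum. By the SAP 9.5 formula, 4 tender and 4 swollen joints, ESR 3 and VAS 10 mm give 1.12 + 0.56 + 0.769 + 0.14 = 2.589. Nor does the concern need such patients: Step 1 shows the dependence above 2.6 as well.
- **Severity is already covered.** Steinbrocker class is a tested factor, and Table 4.4 uses it as severity before treatment. It is a functional class, however, not DAS28, and it does not adjust the other tests.
- **The tests are exploratory.** This is a single-arm survey sized for adverse reactions, and no factor is adjusted for any other. That stands and limits the severity, but the tests are the planned answer to a stated objective.

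Three stronger readings are tempting and not supported.

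- A reader might infer that the trouble lies in patients already below 2.6 and that excluding them cures it. Step 3 shows that it does not.
- A reader might infer that Tables 3.1 and 3.5.2 are equally distorted in opposite directions. Table 3.5.2 is distorted only if the fall depends on baseline, and then less.
- A reader might infer that remission is biased by values taken after Humira was stopped, since the final assessment in SAP section 12 has no on-treatment condition. The documents do not show whether such values exist, how many there are or which way they act, so no conclusion follows.

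**Conclusion.** The concern holds for Table 3.1. The absence of a baseline condition, and of baseline DAS28 as factor or stratifier, is plain in the text, and the direction follows from using an absolute cut-off. The size is not known. Under the assumptions listed it is moderate for a 0.5-point baseline difference between factor levels (about 11–18%) and large for 1.0 point (43–62%). It vanishes if the factor is unrelated to baseline. For Table 3.5.2 the point is secondary and conditional.

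SAP section 10.3 refers to a dataset definition document that was not available. If it contains a baseline rule for remission, that rule belongs in the SAP. The point does not show that any factor result will be wrong, only that the planned output could not distinguish the two explanations.

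**What to change.** 1. **Table 3.1.** Add baseline DAS28-4/ESR category (the four activity categories of SAP 10.3, plus unknown) as a background factor. Beside each unadjusted factor test give one stratified by all four categories (for example Mantel-Haenszel, in its generalised form for factors with more than two levels) or adjusted for continuous baseline DAS28. Do not rely on restriction to baseline ≥2.6 or on a two-level split.
2. **Table 3.5.2.** Give the same stratified comparison as a secondary check.
3. **Description only.** Report remission among patients with baseline ≥2.6, and the number without a baseline value.
4. **Time point.** Name the final assessment for Tables 3.1 and 3.2.1–3.2.3, in line with Table 4.4 item 19. If wanted, footnote how many final values fall after the Humira end date; no further analysis of that question is needed.

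The cost is SAP wording and some programming. The DAS28 components are already collected at baseline (Protocol section 8), and the planned unadjusted results stay in place. Stratification loses a little power, sparse categories contribute little, and patients without a baseline DAS28 drop out of the stratified test.

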## 11. Data-layer separation

Data	Layer separation
Reason for discontinuation	Remission, subtherapeutic response, onset of adverse events, patient's request, no hospital visit (including hospital transfer), other
Reason for switching	Remission, subtherapeutic response, onset of adverse events, patient's request, no hospital visit (including hospital transfer), other
Sex	Male, female, unknown/unspecified
Pregnancy/breastfeeding	Not pregnant/breastfeeding, pregnant, breastfeeding, unknown/unspecified
Age 1	$\leq 6$ years, $>6$ years
Age 2	$<15$ years, $\geq 15$ years and $<65$ years, $\geq 65$ years
Age 3	$<6$ years, $\geq 6$ years and $<11$ , $\geq 11$ years and $<16$ years, $\geq 16$ years and $<21$ years, $\geq 21$ years
Body weight	$<15$ kg, $\geq 15$ kg and $<30$ kg, $\geq 30$ kg, unknown/unspecified
BMI( $\text{kg}/\text{m}^2$ )	$<18.5$ $\text{kg}/\text{m}^2$ , $\geq 18.5$ $\text{kg}/\text{m}^2$ and $<25.0$ $\text{kg}/\text{m}^2$ , $\geq 25.0$ $\text{kg}/\text{m}^2$ and $<30.0$ $\text{kg}/\text{m}^2$ , $\geq 30.0$ $\text{kg}/\text{m}^2$ and $<35.0$ $\text{kg}/\text{m}^2$ , $\geq 35.0$ $\text{kg}/\text{m}^2$ , unknown
Inpatient/outpatient status at the start of Humira treatment	Inpatient, outpatient, unknown/unspecified
Reason for use and type of disease	Generalised arthritis, oligoarthritis (persistent), oligoarthritis (extended), polyarthritis (RF negative), polyarthritis (RF positive), other, unknown/unspecified
Disease duration 1	$<6$ months, $\geq 6$ months and $<1$ year, $\geq 1$ year and $<2$ years, $\geq 2$ years and $<3$ years, $\geq 3$ years and $<5$ years, $\geq 5$ years and $<10$ years, $\geq 10$ years and $<20$ years, $\geq 20$ years, unknown/unspecified
Disease duration 2	$<5$ years, $\geq 5$ years, unknown/unspecified
Race	Japanese, other, unknown/unspecified
Steinbrocker Staging System	Stage I, Stage II, Stage III, Stage IV, unknown/unspecified
Steinbrocker Functional Classification	Class I, Class II, Class III, Class IV, unknown/unspecified
Administration method category	Self-administration, self-administration $\leftrightarrow$ administration by a doctor, administration by a doctor, unknown/unspecified
Past medical history	No, yes, unknown/unspecified
Complications	No, yes, unknown/unspecified
Breakdown of complications	Liver disorder, renal disorder, cardiovascular disorder, blood disorder, respiratory disorder, other
Complication: Liver disorder	No, yes, unknown/unspecified
Complication: Renal	No, yes, unknown/unspecified

Data	Layer separation
disorder	
Complication: Cardiovascular disorder	No, yes, unknown/unspecified
Complication: Blood disorder	No, yes, unknown/unspecified
Complication: Respiratory disorder	No, yes, unknown/unspecified
Complication: Other	No, yes, unknown/unspecified
History of allergy	No, yes, unknown/unspecified
Breakdown of history of allergy	Drug, food, other
Previous medications	No, yes, unknown/unspecified
Breakdown of previous medications	Methotrexate, corticosteroid, NSAIDs, other DMARDs
History of treatment with previous medications (biological products)	No, yes, unknown/unspecified
Breakdown of history of treatment with previous medications (biological products)	Tocilizumab, etanercept, other
Concomitant drugs	No, yes, unknown/unspecified
Breakdown of combination drugs	Methotrexate, corticosteroid, NSAIDs, other DMARDs, other drugs
Tuberculin skin test	Tested, not tested, unknown/unspecified
Quantiferon test (including T-SPOT)	Tested, not tested, unknown/unspecified
Chest x-ray	Tested, not tested, unknown/unspecified
Chest CT	Tested, not tested, unknown/unspecified
Immunology test (tuberculin skin test or Quantiferon test or T-SPOT)	No, yes, unknown/unspecified
Image testing (chest x-ray or chest CT)	No, yes, unknown/unspecified
Prophylactic administration (status of prophylactic administration by	No, yes, unknown/unspecified

Data	Layer separation
implementation status of tuberculosis tests)	
HBs antigen test	Implemented (negative, positive, unknown/unspecified, subtotal), not implemented, unknown/unspecified
HBs antibody test	Implemented (negative, positive, unknown/unspecified, subtotal), not implemented, unknown/unspecified
HBc antibody test	Implemented (negative, positive, unknown/unspecified, subtotal), not implemented, unknown/unspecified
Status of Humira treatment (dosage and administration)	20 mg/2 weeks, 40 mg/2 weeks, 20 mg/2 weeks → 40 mg/2 weeks, other
Number of doses	≥1 to <2 doses, ≥2 to <6 doses, ≥6 to <12 doses, ≥12 doses
Days to the date of the last dosing	1 to 28 days, 29 to 84 days, 85 to 168 days, ongoing at day 169
Dose at the start of Humira treatment	20 mg, 40 mg, 80 mg, other, unknown/undescribed
Dosage and administration category	Dose increase group (20 mg → 40 mg), maintained dose group, other, unknown/unspecified
Self-administration	No, yes, unknown/unspecified
Error caused by self-administration	No, yes, unknown/unspecified
Priority survey item	Infection, tuberculosis, interstitial pneumonia, malignant tumour, congestive cardiac failure, autoimmune disease, pancytopenia, demyelinating disease, administration site reaction
Status of previous medication: biological products	No, yes, unknown/unspecified
Status of previous medication: MTX	No, yes, unknown/unspecified
Status of previous medication: corticosteroid	No, yes, unknown/unspecified
Status of previous medication: NSAIDs	No, yes, unknown/unspecified
Status of previous medication: Other DMARDs	No, yes, unknown/unspecified
Status of concomitant drug: MTX	No, yes, unknown/unspecified
Status of MTX: details	<4 mg/m  /week, ≥4 mg/m  /week and <7 mg/m  /week, ≥7 mg/m  /week

Data	Layer separation
	and <10 mg/m  /week, ≥10 mg/m  /week, dose per body surface area unknown
Status of concomitant drug: corticosteroid	No, yes, unknown/unspecified
Status of concomitant drug: NSAIDs	No, yes, unknown/unspecified
Status of concomitant drug: Other DMARDs	No, yes, unknown/unspecified
Combination therapy for juvenile idiopathic arthritis	No, yes, unknown/unspecified
Combination therapy for juvenile idiopathic arthritis: details	Rehabilitation, other, unknown/undescribed
Duration of combination use of MTX for juvenile idiopathic arthritis	No, yes, unknown/unspecified
Duration of combination use of MTX for juvenile idiopathic arthritis: details	After the start of Humira treatment up to the end date of Humira treatment, at least a dose used during Humira treatment, unknown/unspecified
Timing of onset of adverse events	From the start of treatment and within 4 weeks of treatment, after Week 4 of treatment and within 8 weeks of treatment, after Week 8 of treatment and within 12 weeks of treatment, after Week 12 of treatment and within 16 weeks of treatment, after Week 16 of treatment and within 20 weeks of treatment, after Week 20 of treatment and within 24 weeks of treatment, after Week 24 of treatment

